10.5 Survival Follow-up

All patients will be followed for survival until the last evaluable patient completes 12 months of follow-up.

10.6 Second Course Phase (Pembrolizumab Retreatment Period)

Participants who stop pembrolizumab with SD or better response who then experience radiographic disease progression may be eligible for up to one year of additional treatment with pembrolizumab via the Second Course Phase at the discretion of the investigator if:

- no cancer treatment was administered since the last dose of pembrolizumab,
- the participant meets the safety parameters listed in the Inclusion/Exclusion criteria below, and
- the trial is open.

Participants will resume therapy at the same dose and schedule at the time of initial discontinuation. This retreatment is termed the Second Course Phase of this study and is only available if the study remains open and the participant meets the following conditions:

EITHER

- Stopped initial treatment with pembrolizumab after attaining an investigator-determined confirmed CR according to RECIST 1.1, and
- Was treated for at least 24 weeks with pembrolizumab before discontinuing therapy
- Received at least two cycles of pembrolizumab beyond the date when the initial CR was declared

OR

- Had SD, PR or CR and stopped pembrolizumab treatment for reasons other than disease progression or intolerability

AND

- Experienced an investigator-determined confirmed radiographic disease progression after stopping their initial treatment with pembrolizumab
- Did not receive any anti-cancer treatment since the last dose of pembrolizumab

10.6.1 Has a performance status of 0 or 1 on the ECOG Performance Scale

- Demonstrates adequate organ function as detailed in Section 8.3.
- Female participant of childbearing potential should have a negative serum or urine pregnancy test within 72 hours prior to receiving retreatment with study medication.
- Female participant of childbearing potential should be willing to use 2 methods of birth control or be surgically sterile, or abstain from heterosexual activity for the course of the study through 120 days after the last dose of study medication (Section 9.4.2 Contraception). Participants of child bearing potential are those who have not been surgically sterilized or have been free from menses for > 1 year.
- Male participant should agree to use an adequate method of contraception starting with the first dose of study therapy through 120 days after the last dose of study therapy.
- Does not have a history or current evidence of any condition, therapy, or laboratory abnormality that might interfere with the participant's participation for the full duration of the trial or is not in the best interest of the participant to participate, in the opinion of the treating investigator.

Participants who restart treatment will be retreated at the same dose and dose interval as when they last received pembrolizumab. Treatment will be administered for up to one additional year. Management of all immunotherapy related toxicities are outlined in Section 9.3.1 Supportive Care Guideline. This guideline should be followed in the retreatment period, however, any prior events and subsequent interventions or treatment modification during the initial treatment period should be continued in the retreatment phase. Any patient having sustained immunotherapy induced severe (grade 3) pneumonitis/ colitis / haematologic events etc. corticosteroids for > 12 weeks, or life-threatening events should be excluded from retreatment.

Once any new systemic anti-cancer therapy or, second course of pembrolizumab has been initiated, the participant will have concluded their participation in the treatment phase of the study. On completion of the treatment phase of the study the participant enters the follow-up phase and will be followed up for survival from the date any new treatment starts.

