2 SCHEDULE OF EVENTS

Table 1: Schedule of Events

Trial Period:	Screening Phase	Radiotherapy	Treatment Cycles		Safety Follow-up	Follow-up ¹⁷	Progression (Upon first progression)
Treatment Cycle/Title:	Screening	SABR±CRT ³	Day 1 Cycle 1	Day 1 Cycle 2-8			
Scheduling Window (Days):	-35 to -1	Commence within 4 weeks of registration ³	5 days post SABR ± 3 days	21 days post previous cycle Day 1 ± 3 days	30 days from date of last dose of pembrolizumab ± 3 days	3 months from SABR ± 14 days	
Clinical/Administrative Assessments							
Informed Consent	X						
Inclusion/Exclusion Criteria	X						
Demographics and Medical History	X						
Disease Specific Medical History	X						
SINS score for Spinal Targets	X						
Full Physical Examination	X		X	X			
Directed physical Examination						X	
Vital Signs ¹ and Body Measurements	X		X	X		X	
ECOG Performance Status	X		X	X		X	
Review Adverse Events ²	X		X	X	X	X	X
Radiotherapy planning	X						
Trial Treatment Administration – SABR ³		X					
Trial Treatment Administration – Pembrolizumab ⁴			X	X			See section 10.6
Review Prior/Concomitant Medications	X		X	X			
Numerical Pain Rating Score		X	X	X		X	
New Anti-Cancer Therapy Status / Second phase pembrolizumab					X	X	X
Survival Status ¹⁸						X	
Laboratory Procedures/Assessments: analysis performed by LOCAL laboratory							

Trial Period:	Screening Phase	Radiotherapy	Treatment Cycles		Safety Follow-up	Follow-up ¹⁷	Progression (Upon first progression)
Treatment Cycle/Title:	Screening	SABR±CRT ³	Day 1 Cycle 1	Day 1 Cycle 2-8			
Scheduling Window (Days):	-35 to -1	Commence within 4 weeks of registration ³	5 days post SABR ± 3 days	21 days post previous cycle Day 1 ± 3 days	30 days from date of last dose of pembrolizumab ± 3 days	3 months from SABR ± 14 days	
Pregnancy Test ⁵ – Urine or Serum β-HCG	X		X	X			
Haematology ⁶	X		X	X		As clinically indicated	
Chemistry ^{7,8}	X		X	X			
T3, FT4 and TSH ⁹	X		X	X			
PT/INR and aPTT ¹⁰	X						
HIV, Hepatitis B and C ¹¹	X						
Tumour Evaluation							
Tumour assessment by CT scan or MRI ¹² (Chest, Abdo, Pelvis) reported as per RECIST 1.1	X				X (Every 3 months from SABR)		
CT scan (Brain) (if clinically indicated) ¹²	X			X (Cycle 4 & 8 only)		As clinically indicated	
Whole body bone scan (if clinically indicated) ¹²	X			X (Cycle 4 & 8 only)		As clinically indicated	
Metastatic FFPE Biopsy ¹³	X					X (month 9 only)	X
Primary Surgery FFPE sample ¹⁴	X						
Blood Serum Sample		X	X	X		X (9, 12 and 24 months)	X

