Whole Blood Sample ^{15,16}		X	X	X		X (9, 12 and 24 months)	X

Clinical/Administrative Assessments

- Vital signs include blood pressure, heart rate, respiratory rate and temperature. Height will be measured at screening only.
- Baseline abnormalities (using CTCAE v4.03) must be recorded from signature of informed consent to prior to start of treatment. Adverse events (using CTCAE v4.03) are then required to be assessed on day 1 of every pembrolizumab cycle and at 30 days following last pembrolizumab treatment. SABR related adverse events will be collected at every subsequent follow-up visit until 2 years after completion of SABR.

3. Conventional hypofractionated radiotherapy of **30-36Gy** may be delivered to individual lesion(s) if SABR is determined to be not technically or safely possible to deliver. If CRT is required it must be completed prior to SABR administration. **At least one lesion must receive SABR.**

4. Pembrolizumab should be administered at 5 days (+/- 3 days) of the last SABR treatment for a total of 8 cycles.

Laboratory Procedures/Assessments – All diagnostic laboratory tests should be performed within 10 days of study registration (to determine eligibility), and also within 3 days prior to every cycle of pembrolizumab (unless indicated otherwise below)

5. Urine or serum pregnancy test for patient of childbearing potential should be performed within 7 days of study registration and also 72 hours within first dose of pembrolizumab. If the urine test is positive or cannot be confirmed as negative, a serum pregnancy test will be required.

6. Haematology: Haematocrit, haemoglobin, platelet count, white blood cell count (total and differential), red blood cell count, absolute neutrophil count and absolute lymphocyte count.

7. Chemistry: Carbon dioxide (if considered standard of care only), uric acid, calcium chloride, glucose, phosphorus, potassium, sodium, magnesium, total protein.

8. Liver Function Tests: Albumin, Alkaline Phosphatase (ALP), Alanine Aminotransferase (ALT), Aspartate Aminotransferase (AST), Lactate Dehydrogenase (LDH), Gamma-Glutamyl Transferase (GGT, total bilirubin and direct bilirubin if total bilirubin is elevated above the ULN), Kidney Function Tests: Urea, creatinine.

9. Thyroid Function: T3, T4 and TSH.

10. Coagulation Profile: PT (INR), aPTT. These need only be done if there is clinical concern regarding patient anticoagulation.

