17. Study Follow-Up Visits - follow-up assessments (e.g visits @ 1, 3, 6, 9, 12, 15, 18, 21 and 24 months post end of SABR Treatment) should be undertaken within \pm 14 days of the scheduled time point. In the event of overlapping visits (i.e. between day 1 of each pembrolizumab cycle and post-SABR follow-up visits), only one visit is required but all protocol mandated investigations (for both timepoints) must be undertaken.

18. All patients will be followed for survival until the last evaluable patient completes 12 months of follow-up. Participants who start a new systemic therapy, are retreated with pembrolizumab or who have distant progression will be followed for survival only.

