9.2.2 Prohibited Concomitant Medications

Participants are prohibited from receiving the following therapies during the Screening and Treatment Phase (including retreatment for post-complete response relapse) of this trial:

- Antineoplastic systemic chemotherapy or biological therapy
- Immunotherapy not specified in this protocol
- Chemotherapy not specified in this protocol
- Investigational agents other than pembrolizumab
- Live vaccines within 30 days prior to the first dose of trial treatment and while participating in the trial. Examples of live vaccines include, but are not limited to, the following: measles, mumps, rubella, varicella/zoster, yellow fever, rabies, BCG, and typhoid vaccine.
- Systemic glucocorticoids for any purpose other than to modulate symptoms from an event of clinical interest of suspected immunologic etiology. The use of physiologic doses of corticosteroids may be approved after consultation with the Sponsor. The regular use of steroid prophylaxis > 10 mg daily for flare reaction on the day of SABR delivery is permitted.

Participants who, in the assessment by the investigator, require the use of any of the aforementioned treatments for clinical management should be removed from the trial. Participants may receive other medications that the investigator deems to be medically necessary.

The Exclusion Criteria describes other medications which are prohibited in this trial.

There are no prohibited therapies during the Post-Treatment Follow-up Phase.

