10.1.10 Adverse Event (AE) Monitoring

The investigator or qualified designee will assess each participant to evaluate for potential new or worsening AEs as specified in the Schedule of Events and more frequently if clinically indicated. Adverse experiences will be graded and recorded throughout the study and during the follow-up period according to NCI CTCAE Version 4.03. AEs will be characterized in terms regarding seriousness, causality, toxicity grading, and action taken with regard to trial treatment.

Please refer to Section 10.7 for detailed information regarding the assessment and recording of AEs.

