10.4 Follow-up Visits

Participants who discontinue trial treatment for a reason other than disease progression will move into the Follow-Up Phase and should be assessed every 3 months by radiologic imaging to monitor disease status until the last evaluable patient completes 12 months of follow-up. Every effort should be made to collect information regarding disease status until the start of new systemic therapy, death, end of the study or if the participant begins retreatment with pembrolizumab as detailed in Section 10.6: Second Course Phase. Information regarding post-study anti-neoplastic treatment will be collected if new treatment is initiated. Participants who start a new systemic therapy, are retreated with pembrolizumab or have distant progression will be followed for survival only.

Participants who are eligible to receive retreatment with pembrolizumab according to the criteria in Section 10.6 Second Course Phase will move from the follow-up phase to the Second Course Phase when they experience disease progression.

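### Patients retreated with trial pembrolizumab go to survival-only follow-up, against the rule for adverse event review at every pembrolizumab cycle, and no Second Course schedule settles which applies

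*Combined protocol and SAP*

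**What the plan says.** Section 10.6 lets patients who stopped with stable disease or better, and then progressed, resume the drug. They "may be eligible for up to one year of additional treatment with pembrolizumab via the Second Course Phase", at the same dose and interval. Once that course starts, the treatment phase is over and "the participant enters the follow-up phase and will be followed up for survival from the date any new treatment starts".

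Footnote 18 to the Schedule of Events is more restrictive: "Participants who start a new systemic therapy, are retreated with pembrolizumab or who have distant progression will be followed for survival only". Section 10.4 repeats the rule almost word for word.

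The AE rules are not limited to the initial course. Footnote 2 requires AE assessment on "day 1 of every pembrolizumab cycle and at 30 days following last pembrolizumab treatment". Section 10.1.10 says: "Adverse experiences will be graded and recorded throughout the study and during the follow-up period according to NCI CTCAE Version 4.03". Section 10.8.1 runs AE recording to 30 days after pembrolizumab is completed, and it expressly covers events in the follow-up phase.

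Table 1 has treatment columns for cycle 1 and cycles 2 to 8 only. Its progression column has one AE review, and for pembrolizumab it says "See section 10.6". Section 10.6 gives eligibility, dose and toxicity management, but no visits and no AE reviews. The safety analysis in 11.2.3 does not mention the Second Course.

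**The concern.** Safety is the sole primary objective, and 11.2.3 reports the proportion of patients with grade 3 or higher toxicity. Under the definitions in 10.8.5, a grade 3 event is not serious merely because of its grade; it needs hospitalisation or another listed criterion. A grade 3 event managed in clinic therefore depends on routine AE recording, and that is what the survival-only rule appears to switch off.

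Two sites could each follow the protocol and return different AE data for the same retreated patient. Events that were never recorded may not be recoverable at the analysis, and 11.2.3 does not say whether recorded ones count.

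**Working it through.** No figure in the plan is disputed. The check compares the rules and counts the doses and reviews that they govern.

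**Rules side by side, for a patient in the Second Course**

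| Question | Survival-only text | AE text |
|---|---|---|
| Phase | Treatment phase concluded, follow-up for survival (10.6) | AEs recorded in the follow-up phase as well (10.8.1) |
| AE review at each dose | None (footnote 18, 10.4) | Day 1 of each pembrolizumab cycle (footnote 2) |
| End of AE recording | At the start of retreatment, by implication | 30 days after pembrolizumab (footnote 2, 10.8.1) |
| Second Course schedule | None in Table 1 or 10.6 | None in Table 1 or 10.6 |
| Place in the analysis | Not stated (11.2.3) | Not stated (11.2.3) |

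No sentence ranks one set of rules above the other.

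**Doses**
- Initial course: 8 cycles × 3 weeks = 24 weeks, which agrees with the plan's figure of about 6 months.
- Second Course: up to one year at 21-day intervals. Doses fall on days 0, 21, 42 and so on; the last within 365 days is on day 17 × 21 = 357, so the maximum is 17 + 1 = 18 doses.
- Full exposure: 8 + 18 = 26 doses, and 26 / 8 = 3.25 times the initial course.

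**Scheduled AE reviews**
- Initial course: 8 day-1 reviews + 1 thirty-day visit = 9.
- Full Second Course under footnote 2: 18 + 1 = 19.
- Full Second Course under survival-only follow-up: 0.

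**How far the maximum can be reached.** The final analysis falls 12 months after the last participant's SABR. For that participant, assume no dose delays and progression confirmed 28 days after the scan:
- Month-6 progression: start on day 182 + 28 = 210; doses by day 365 = 8.
- Month-9 progression: start on day 274 + 28 = 302; doses by day 365 = 4.
- Month-12 progression: start on day 365 + 28 = 393; doses by day 365 = 0.

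Patients enrolled earlier can receive more. Eighteen is a ceiling for one patient, not an expected value.

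**What continues under either reading**
- Serious events: all-cause reporting to 90 days after pembrolizumab or the final protocol treatment, and related events at any time (10.8.5, 10.8.5.1).
- Toxicity management: the supportive care guideline applies in retreatment (10.6).
- Laboratory tests: entry tests, and results reviewed before each dose of trial treatment (10.1.15).

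What remains unsettled is the recording of non-serious AEs, including non-serious grade 3 events.

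**The case against.** The strongest reply is that the passages can be reconciled. Footnote 18 hangs on the survival status row of Table 1. In 10.4 the survival-only sentence closes a paragraph on imaging, disease status and later therapy. Section 10.6 moves the retreated patient into the follow-up phase, and 10.8.1 keeps AE recording alive there. On this reading, survival-only follow-up ends disease assessment and nothing else. That may well be the intent. It does not remove the word *only* or supply a schedule, and footnote 18 groups retreated patients with those who leave for another systemic therapy. A site could reasonably stop its AE forms.

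Several stronger readings are tempting, and the documents do not support them:
- *Retreated patients are unmonitored.* They are not, given the provisions that continue.
- *Serious event reporting stops because the Second Course is a new anti-cancer therapy.* Footnote 18, 10.4 and 10.6 list retreatment separately from new systemic therapy, and 10.6 calls it a phase of this study. On the ordinary reading, reporting continues.
- *Section 9.2.2 settles the conflict.* It does place post-complete-response retreatment "during the Screening and Treatment Phase (including retreatment for post-complete response relapse) of this trial", but only to define prohibited medications. It says nothing about AE collection.
- *The acute and long-term AE results would change.* Sections 7.14 and 10.8.2 do not say which course closes the acute window, but 11.2.3 plans no acute or late table, so no planned output depends on it.
- *The grade 3 or higher rate is biased by a known amount.* The documents give no retreatment rate and no AE rate during retreatment, so no shift can be estimated.

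**Conclusion.** The conflict stands as a minor point. For a patient in the Second Course, the protocol both requires AE review at every pembrolizumab cycle and restricts follow-up to survival, with no schedule to decide between them. The difference is up to 19 scheduled AE reviews against none for a fully retreated patient, over up to 18 doses. That count assumes a full year of retreatment at exact 3-week intervals.

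The consequence is confined to non-serious AEs in retreated patients, whose number is unknown. Retreatment is at the investigator's discretion and needs ECOG 0 or 1, adequate organ function and an open trial. The analysis is descriptive, and sample size is unaffected. The 12-patient stopping review, which follows 12 weeks of pembrolizumab, is essentially untouched. The point still merits correction because the missing data would bear on the only primary objective.

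**What to change.** 1. In footnote 18, 10.4 and 10.6, state that survival-only follow-up ends disease assessment. It does not end AE recording to 30 days, or serious event reporting to 90 days, after the last dose of trial pembrolizumab, including the Second Course.
2. Add a Second Course column to Table 1 with day-1 AE review and a 30-day safety visit.
3. In 11.2.3, either tabulate Second Course AEs separately beside the initial-course grade 3 or higher proportion, or state that they are included in it.

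The cost is a short amendment, AE forms for a few patients who already attend every 3 weeks for infusions, and one extra table if the separate option is chosen. That option limits the headline proportion to the initial course, a restriction that 11.2.3 does not now contain. Second Course toxicity would then sit outside the headline, so the two results must be shown together.

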10.7 Assessing and Recording Adverse Events

An adverse event is defined as any untoward medical occurrence in a patient or clinical investigation participant administered a pharmaceutical product (or any other protocol specified intervention including radiation therapy, surgery or use of a device) and which does not necessarily have to have a causal relationship with this treatment. An adverse event can therefore be any unfavourable and unintended sign (including an abnormal laboratory finding, for example), symptom, or disease temporally associated with the use of a medicinal product or protocol-specified procedure (including radiation therapy, surgery or use of a device), whether or not considered related to the medicinal product or protocol-specified procedure.

Any worsening (i.e., any clinically significant adverse change in frequency and/or intensity) of a pre-existing condition that is temporally associated with the use of the medicinal product, (or associated with the use of any other protocol specified intervention including radiation therapy, surgery or use of a device), is also an adverse event.

Adverse events may occur during the course of the use of protocol treatment in clinical trials or within the follow-up period specified by the protocol, or prescribed in clinical practice, from overdose (whether accidental or intentional), from abuse and from withdrawal.

Adverse events may also occur in screened participants during any pre-allocation baseline period as a result of a protocol-specified intervention, including washout or discontinuation of usual therapy, diet, placebo treatment or a procedure.

Progression of the cancer under study is not considered an adverse event unless it is considered to be drug related by the investigator.

10.8 Attribution of cause of an Adverse Event

The causal relationship to protocol treatment (attribution), as assessed by the Investigator is also to be recorded. Attribution of cause requires at least a reasonable possibility of a causal relationship between the event and the use of the investigational drug or any other protocol-specified intervention.

All protocol-specified interventions (including pharmaceutical products, radiation therapy, surgery or use of a device) administered prior to the date of the event must be attributed a degree of causality from one of the following codes:

- Definite: The AE is clearly related to protocol treatment
- Probable: The AE is likely related to protocol treatment
- Possible: The AE is may be related to protocol treatment
- Unlikely: The AE is doubtfully related to protocol treatment
- Unrelated: The AE is clearly NOT related to protocol treatment

An AE **does not** include:

- Medical or surgical procedures (e.g. surgery, endoscopy, tooth extraction, transfusion); the condition that leads to the procedure is an AE
- Pre-existing diseases or conditions present or detected prior to start of study product administration, that do not worsen
- Situations where an untoward medical occurrence has not occurred (e.g. hospitalisation for elective surgery, social and/or convenience admissions)
- Overdose of either study product or concomitant medication without any signs or symptoms unless the subject is hospitalised for observation.
- Progression of the disease under study

